18. DATA HANDLING AND RECORD KEEPING

18.1 Data Management Responsibilities

Data are entered in a validated database. The internal consistency and data integrity of the study database are defined by a validated set of checks defined and documented in the Study Validation Plan. A deviation from this set of pre-defined computerized checks creates a discrepancy which can be handled using the Clinical Data Management System application. Data queries will be generated and resolved. Adverse events will be coded with MedDRA version 19.0 and concomitant therapies with WHO-DD version of December 2011.

18.2 Electronic Data Capture Methods

Electronic CRF is used to record study data and it is an integral part of the study and subsequent reports. Therefore, the eCRF must be completed for each Patient included in the study. Each Patient will be given a specific Patient number. Patient data will be recorded in the eCRF using this number and will not be known in any other way to any person other than the parties involved in conducting and regulating the study.

18.3 Schedule and Content of Reports

A final Clinical Study Report will be prepared according to ICH E3 Guidelines.

18.4 Study Records Retention

The Investigator will maintain all study records according to ICH-GCP and applicable regulatory requirements. Records will be retained for at least two years after the last marketing application approval or two years after formal discontinuation of the clinical development of the investigational product or according to applicable regulatory requirements. If the Investigator withdraws from the responsibility of keeping the study records, custody must be transferred to a person willing to accept the responsibility.

18.5 Protocol Deviations

Any not purely formal, significant change of the approved protocol will be documented and explained. As soon as possible, the implemented deviation or change, the reasons for it, and, if appropriate the proposed protocol amendment(s) will be submitted:

- to the IRB/IEC for review and approval/favorable opinion,
- to the Sponsor for agreement, and
- to the regulatory authorities, if needed.

The Investigator will implement a deviation from or a change of the protocol to eliminate immediate hazards to the trial Patients without prior approval/favorable opinion of the IRB/IEC.

19. USE OF INFORMATION AND PUBLICATION

All information obtained during the course of this study will be regarded confidential and the property of the Sponsor. The Investigators agree not to disclose such information in any way without prior written permission from the Sponsor.

The information obtained from the clinical study will be disclosed to regulatory authorities, other Investigators, corporate partners, or consultants as required.

The clinical study is planned to be registered on clinicaltrials.gov public database within 1 month after study start and to be kept updated throughout the entire study period.

1 ABBREVIATIONS

AE	Adverse Event
ALT	Alanine Aminotransferase
AST	Aspartate Aminotransferase
ATC	Anatomical Therapeutic Chemical
BIL	Bilirubin
BUN	Blood Urea Nitrogen
CRA	Clinical Research Associate
CRO	Contract Research Organization
CRP	C-reactive Protein
(N)CS	(Not) Clinically significant
DSMB	Data Safety Monitoring Board
eCRF	Electronic Case Report Form
ESR	Erythrocyte Sedimentation Rate
FAS	Full-analysis set
GCP	Good Clinical Practice
Hb	Hemoglobin
HC	Hematocrit
HD	Hospital Discharge
ICH	International Conference on Harmonization
ICU	Intensive Care Unit
IEC	Independent Ethics Committee
IMP	Investigational medicinal Product
INR	International Normalized Ratio
IRB	Institutional Review Board
ITT	Intention-to-treat
ICU	Intensive Care Unit
LDH	Lactate Dehydrogenase

	STATISTICAL ANALYSIS PLAN	FSTAT.01.03
Study Code: HEM-HEM-01-17		Sealantium Medical Ltd.

LOS	Length of Stay
MCH	Mean Cell Hemoglobin
MCHC	Mean Cell Hemoglobin Concentration
MCV	Mean Corpuscular Volume
MedDRA	Medical Dictionary for Regulatory Activities
MRI	Magnetic Resonance Imaging
OR	Operating Room
PD	Protocol Deviation
PLT	Platelets
PM	Project Manager
PPS	Per-Protocol Set
PT	Preferred Term
RBC	Red Blood Cells
SAE	Serious Adverse Event
SAF	Safety Analysis Set
SAP	Statistical Analysis Plan
SGOT	Serum Glutamic Oxaloacetic Transaminase
SGPT	Serum Glutamic Pyruvic Transaminase
SOC	System Organ Class
TBS	Target Bleeding Site
TEAE	Treatment-emergent Adverse Event
TEG	Thrombelastography
TTHP	Time to Hemostasis from First Product Application
TTHR	Time to Hemostasis from Patient Randomization
WBC	White Blood Cells
WHO	World Health Organization

	STATISTICAL ANALYSIS PLAN	FSTAT.01.03
Study Code: HEM-HEM-01-17	Sealantium Medical Ltd.	

2 GENERAL

This statistical analysis plan (SAP) describes the statistical methods to be used during the analysis and reporting of data collected under Sealantium Medical Ltd Study Protocol HEM-01-17 version 5.0 dated 8th July 2021. This SAP should be read together with the Study Protocol, *annotated eCRF* (V 5.0), *Data Management Plan* (V 3.1) and *Data Monitoring Plan* (V 3.0).

This Statistical Analysis Plan will be finalized after the blind data review meeting before locking the study database.

In the Appendix 1 and Appendix 2 are reported shells for Listing and Tables, respectively.

3 STUDY DETAILS (AS PER STUDY PROTOCOL)

3.1 Study Design

This is a Phase I/II randomized, prospective, controlled, multi-center, open-label, two-arms study evaluating the safety and preliminary efficacy of sFilm-FS in controlling liver bleeding during elective surgery, when conventional methods of control are ineffective or impractical.

The surgical procedure was performed as per standard of care at the investigational site. A target bleeding site (TBS) was to be identified intra-operatively by the Investigator following transection of the hepatic parenchyma.

Target Bleeding Site (TBS) was defined as the first bleeding site in which conventional methods of bleeding control (i.e., suture, ligature, cautery) are ineffective or impractical. The TBS had to be a site where occlusion of the injured surface blood vessels is required to achieve hemostasis. It had to be possible to cover the TBS adequately, with an appropriate overlap, using a single unit of product (sFilm-FS or TACHOSIL®). This excluded bleeding from large defects in large arteries or veins requiring repair.

The TBS was the only site or region to be evaluated for hemostasis in this clinical study. If additional bleeding sites/regions requiring a topical hemostatic product was identified after the treatment of the initial target bleeding site, these bleeding sites were to be treated with the same study medication according to the patient's randomization assignment, if clinically appropriate. These areas were not to be assessed for hemostasis, but information was collected.

Once the TBS was identified (intra-operatively), the Investigator had to immediately enroll and randomize the patient into one of the following treatment arms (according to Inclusion/exclusion criteria reported in the paragraphs 8.2 and 8.3 of the study protocol):

	STATISTICAL ANALYSIS PLAN	FSTAT.01.03
Study Code: HEM-HEM-01-17	Sealantium Medical Ltd.	

- **Group A** (investigational product): sFilm-FS was applied at the target bleeding site immediately after conventional methods of control were exhausted. The sFilm-FS had to adequately cover the entire target bleeding site. After application of sFilm-FS, the Investigator immediately applied manual compression continuously for at least 2 minutes. A surgical sponge had to be used to assist in providing adequate pressure. Hemostasis was assessed after carefully releasing the compression at the site. sFilm-FS was not to be removed once bleeding has stopped. A maximum of 4 units of sFilm-FS were to be used per patient.
- **Group B** (active comparator): TACHOSIL® was applied at the target bleeding site immediately after conventional methods of control have been exhausted. TACHOSIL® had to be applied as per the approved prescribing information, with a manual compression of at least 3 minutes. A maximum of 4 units of TACHOSIL® were to be used per patient.

Patients were randomized with a 1:1 allocation ratio to either sFilm-FS (investigational product) or TACHOSIL® (active-comparator).

Patients were then monitored for a total period of 6 months following surgery. Patients were evaluated at study site at Screening Visit (Visit 1, between Day -21 and Day -1), Visit 2 (1 day before surgery), Visit 3 (Day 0, the day of surgery), Visit 4 (daily assessments post-surgery until the day before hospital discharge), Visit 5 (assessments post-surgery, at the day of hospital discharge), Visit 6 (follow-up visit 1; at 30 ± 3 days post-surgery), Visit 7 (follow-up visit 2; at 60 ± 7 days post-surgery), Visit 8 (follow-up visit 3; at 120 ± 14 days post-surgery), and Visit 9 (follow-up visit 4; at 180 ± 14 days post-surgery). Monitoring of patients included a list of evaluations, including vital signs, physical examination, blood, and urine sampling, MRI assessment, evaluation of antibodies for Human Fibrinogen and Human Thrombin, recording of adverse events, transfusion requirements and concomitant medications, as indicated in the Schedule of Assessments (Table 1). Efficacy assessment were to be evaluated intra-operatively by evaluation of hemostasis before patient's surgical closure.

The study was monitored by an independent Data Safety Monitoring Board (DSMB – paragraph 7.4 of Study protocol). The DSMB had the responsibility for the review of data and identification of any potential safety issues throughout the study. If necessary, the DSMB suggested recommendations regarding protocol revisions, and recommended whether the study had to proceed on the basis of safety data considering established stopping rules (refer to paragraph 7.3.2 of Study Protocol).

Study Code: HEM-HEM-01-17

Sealantium Medical Ltd.

Visit Type	Screening	Baseline	Surgery	Post-Surgery to Hospital Discharge (HD)	Hospital Discharge (HD)	Follow-Up #1	Follow-Up #2	Follow-Up #3	Follow-Up #4
Visit N.**	1	2*	3	4	5	6	7	8	9
Study Day	D-21 to D-1	D-1	D0	Daily from D1 to D-HD	D-HD	D30 (±3)	D60 (±7)	D120 (±14)	D180 (±14)
Informed Consent collection	x								
Inclusion/Exclusion Criteria evaluation	x	x	x						
Demographics/Medical History	x								
Physical Examination	x	x			x	x	x	x	x
Vital signs ¹	x	x	x	x ¹¹	x	x	x	x	x
Pregnancy test ²	x	x							
Blood hematology & biochemistry ³	x	x	x	x ¹¹	x	x	x	x	x
Urine analysis ⁴	x	x	x		x	x			x
Coagulation (PT, PTT, INR)	x	x	x		x	x			x
Serum sample collection ⁵	x								
Antibodies testing ⁶	x					x			x
MRI assessment ⁷	x								x
Randomization			x						
Product application			x						
Operative/Surgical information collection ⁸			x						
Intra-operative details collection ⁹			x						
Determination of hemostasis at TBS ¹⁰			x						
Use of other hemostatic measures			x						
Adverse Events			x	x	x	x	x	x	x
Transfusion requirements			x	x	x	x	x	x	x
Bleeding, thrombotic, and transfusion-related complications			x	x	x	x	x	x	x
Concomitant medications	x	x	x	x	x	x	x	x	x

Table 1: Study flow chart

STATISTICAL ANALYSIS PLAN

FSTAT.01.03

Study Code: HEM-HEM-01-17

Sealantium Medical Ltd.

* V2 to be skipped in case V1 is performed one day before surgery (D-1).

** All patients can request or be requested to be evaluated in an additional visit (i.e., in case of suspected adverse events).

¹ Vital signs will include blood pressure, heart rate, temperature, and respiratory rate.

² β-HCG urine pregnancy tests will be conducted in case of patients with childbearing potential.

³ Blood hematology and biochemistry tests include: Hb, HC, MCH, MCHC, MCV, RBC, WBC, PLT, Fibrinogen, lactate, D-Dimer, AT, ESR, CRP, BUN, creatinine, uric acid, BIL, LDH, AST (SGOT), ALT (SGPT), Gamma-GT, Na, Ca, P, glucose, albumin, total protein.

⁴ Urine analysis tests include: specific gravity, pH, glucose, protein, blood, ketones, microscopic examination.

⁵ A serum sample will be collected and stored at -70°C for possible future viral safety testing.

⁶ Measurement of levels of antibodies against Human Fibrinogen and Human Thrombin. For this purpose, a serum sample will be collected and stored at -70°C for testing at the end of the study.

⁷ Additional MRI will be performed throughout the study if the investigator identifies signs and symptoms of unanticipated or unexpected persistent inflammatory response, or unexplained abdominal pain or other symptoms (for instance signs of adhesions, bowel obstruction, etc.).

⁸ Operative/surgical information include OR time, procedure time, time from liver resection/incision to initiation of fascial closure, drain usage, estimated blood loss, cell salvage use, transfusion information (if applicable), length of stay (ICU and overall LOS).

⁹ Intra-operative details include hepatic parenchyma classification type (normal or abnormal, steatotic, cirrhotic or other), Investigator description of the TBS (area, density, arterial/venous/mixed, intensity of flow), alternative methods used to achieve hemostasis (if applicable), estimated TBS treated area and total resected area, number of product units applied at the TBS and at other areas rather than the TBS, incidence of post-operative bile leaks requiring intervention, hepatic segment information (anatomic resection/non-anatomic resection).

¹⁰ Patients will be monitored for absence of bleeding at 2, 3, 5, 7, and 10 minutes after product application and thereafter, before closing the site.

¹¹ Assessments to be taken daily from one day after surgery (D1) until hospital discharge (D-HD).

	STATISTICAL ANALYSIS PLAN	FSTAT.01.03
Study Code: HEM-HEM-01-17		Sealantium Medical Ltd.

3.2 Study Objectives

The primary objective of this study is to evaluate the safety of sFilm-FS versus inactive comparator (TACHOSIL®) when used as adjunct to conventional hemostatic techniques during elective surgery in which liver bleeding is encountered.

The secondary objective of this study is to preliminarily evaluate the hemostatic efficacy of sFilm-FS in controlling liver bleeding during elective surgery.

3.3 Study Endpoints

3.3.1 Primary Endpoint

The primary endpoint of the study consists of multiple safety variables as a composite marker for the safety. Variables of the composite marker were assessed during all study periods: from randomization to end of follow-up. It includes evaluation of treatment emergent adverse events (TEAEs), particularly TEAEs related to bleeding at TBS, thrombotic events, transfusion-related complications, post-operative adhesions (MRI assessment). It also includes evaluation of vital signs, physical examination, urine analysis, blood/coagulation parameters profiles, antibodies against fibrinogen and thrombin, and signs of systemic inflammation.

Primary endpoint is considered as a composite endpoint, because it includes multiple explanatory variables that support safety and tolerability of study treatment on the efficacy claim.

3.3.2 Secondary Endpoints

The secondary endpoints of the study are:

- The proportion of patients achieving hemostasis at TBS: at 2 (for sFilm-FS product only) 3, 5, 7 or 10 minutes following first product application, without the occurrence of re-bleeding, starting from 10 minutes after product application and until the completion of surgical closure. Hemostasis at TBS is defined as: absence of bleeding without the occurrence of re-bleeding.
- The incidence of re-treatment (defined as one or more additional patch of sFilm-FS or TACHOSIL®) at the TBS at the different time points (2 for sFilm-FS only, 3, 5, 7, 10 minutes from first product application).
- The Time to Hemostasis from first product application (TTHP).
- The proportion of all patients that have achieved hemostasis 10 minutes after first product application and therefore did not need to convert to standard of care treatment at the end of these 10 minutes. This includes all patients that achieved hemostasis with a single patch application and patients that required additional patches.
- The incidence of treatment failure. Treatment failure is defined as follows:

	STATISTICAL ANALYSIS PLAN	FSTAT.01.03
Study Code: HEM-HEM-01-17	Sealantium Medical Ltd.	

1. in case the bleeding at TBS (or re-bleeding) is still observed after 10 minutes following first application of product
2. if hemostasis at TBS is achieved, but the Investigator decides that and additional treatment is required to ensure the durability of hemostasis
3. if there is a breakthrough bleeding requiring treatment other than the product, at any time

From treatment failures definition are excluded those re-bleeding arising from the target bleeding site after hemostasis has been reached, and that are caused by movement of patch from the wound (caused by the surgeon or any other possible external factor) or other external factors. These cases should be regarded as Adverse Events rather than treatment failures. See Sponsor MEMO "*Clarification on treatment failure vs AE*" (AE=adverse event) dated 12th April 2022.

- The incidence of transfusion requirements in the 6 months follow-up period.

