Secondary Endpoints	
The secondary endpoints of the study are related to product hemostatic efficacy. For this purpose, hemostasis and treatment failure are defined.
 
Hemostasis is defined as an absence/cessation of bleeding at the target bleeding site (TBS) according to the surgeon's judgement, so that the surgical closure of the field could be started.
 
Treatment failure is defined as follows:
 
 - in case the bleeding at TBS (or re-bleeding) is still observed after 10 minutes following first application of study product; - if hemostasis at TBS is achieved, but the Investigator decides that an additional treatment is required to ensure the durability of hemostasis; - if there is a breakthrough bleeding requiring treatment other than the study product, at any time

Secondary Endpoints	
Secondary endpoints include:
 
 • Proportion of patients achieving hemostasis at TBS at 2 (applicable only for sFilm-FS), 3, 5, 7 or 10 minutes following first product application, without the occurrence of re-bleeding, starting from 10 minutes from first product application and until the completion of surgical closure. • Incidence of re-treatment (one or more additional patch of sFilm-FS or TACHOSIL®) at the TBS at the different time points (2 for sFilm-FS, 3, 5, 7, 10 minutes from first product application). • Time to Hemostasis from first product application (TTHP). Time to Hemostasis from patient randomization (TTHR) will be collected as well but will not be used as endpoint. • Percentage of total patients (patients that achieved hemostasis with a single patch application and patients that required additional patches) that have achieved hemostasis 10 minutes after first product application and therefore did not need to convert to standard of care treatment at the end of these 10 minutes. • Incidence of treatment failure based on pre-defined treatment failure criteria (see definition in Section 11.1.3 of the protocol). • Incidence of transfusion requirements in the 6 months follow up period.
Sample Size	
The sample size will be of 30 patients completing the study. 15 patients will be included in the experimental treatment arm (Group A) and 15 patients in the active-comparator arm (Group B) to allow an adequate comparison between treatments. Dropped patients during the course of the study will be replaced.

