Hemostasis is defined as an absence/cessation of bleeding at the TBS according to the surgeon's judgement, so that the surgical closure of the field could be started. Time to hemostasis (TTH) is defined as time until hemostasis is achieved. **TTHP** will be considered as time from first product application and **TTHR** as time from randomization will be collected as well but will not be used as endpoint.

Treatment failure is defined as follows:

- in case the bleeding at TBS (or re-bleeding) is still observed after 10 minutes following first application of product;
- if hemostasis at TBS is achieved, but the Investigator decides that an additional treatment is required to ensure the durability of hemostasis;
- if there is a breakthrough bleeding requiring treatment other than the product, at any time.

In case of treatment failure, the Investigator may revert the treatment to standard of care. If additional sites requiring a topical hemostasis product are identified after the treatment of the initial target bleeding site, these bleeding sites should be treated with the same treatment article according to the patient's randomization assignment, if clinically appropriate. If other hemostatic products are needed, the Investigator should revert to his/her standard of care (excluding fibrin sealants or topical thrombin).

The following information will be collected during surgery and recorded on the eCRF and in the study file:

- Determination of hemostasis at TBS.
- Use of other hemostatic measures.
- Collection of intra-operative details including hepatic parenchyma classification type (normal or abnormal, steatotic, cirrhotic or other), Investigator description of the TBS (area, density, arterial/venous/mixed, intensity of flow), alternative methods used to achieve hemostasis (if applicable), estimated TBS treated area and total resected area, number of product units applied at the TBS and at other areas rather than the TBS, incidence of post-operative bile leaks requiring intervention, hepatic segment information (anatomic resection/non-anatomic resection).
- Collection of operative/surgical information, including OR time, procedure time, time from liver resection/incision to initiation of fascial closure, drain usage, estimated blood loss, cell salvage use, transfusion information (if applicable), length of stay (ICU and overall LOS).

Additional assessments will be taken at the end of surgery and will include the following:

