14.8.2 Secondary Endpoints

The secondary endpoints of the study are:

- Proportion of patients achieving hemostasis at TBS (absence of bleeding) at 2 (for sFilm-FS product only), 3, 5, 7 or 10 minutes following first product application, without the occurrence of re-bleeding starting from 10 minutes after product application and until the completion of surgical closure.
- Incidence of re-treatment (one or more additional patch of sFilm-FS or TACHOSIL[®]) at the TBS at the different time points (2 for sFilm-FS, 3, 5, 7, 10 minutes from first product application).
- Time to Hemostasis from first product application (TTHP). Time to Hemostasis from patient randomization (TTHR) will be collected as well but will not be used as endpoint.
- Percentage of total patients (patients that achieved hemostasis with a single patch application and patients that required additional patches) that have achieved hemostasis 10 minutes after first product application and therefore did not need to convert to standard of care treatment at the end of these 10 minutes.
- Incidence of treatment failure, based on pre-defined treatment failure criteria (see definition in Section 11.1.3 of the protocol).
- Incidence of transfusion requirements in the 6 months follow up period.

Descriptive efficacy analyses will be summarized separately by treatment arm.

Primary analyses will calculate the proportion of patients achieving hemostasis at 3 minutes among the sFilm-SF treatment arm. With 15 patients randomized to sFilm-SF, reasonable confidence intervals (CI) can be estimated. For example, if 80% of the patients achieve hemostasis at 3 minutes (similar to a TACHOSIL[®] reported values of 81% for this endpoint), the accompanying 95% confidence interval (CI) is 52% to 96% (using exact confidence limits). This CI provides evidence that greater than 52% of patients with similar conditions will achieve hemostasis at 3 minutes. This will also be reported for the 15 patients randomized to the TACHOSIL[®] arm. There will be no formal comparison between the two-arms.

Similarly, proportions of patients and corresponding 95% CIs will be estimated for all of the following, separately by treatment arm:

- achieving hemostasis at TBS at each remaining time point,
- incidence of re-treatment (separately by time),
- incidence of treatment failure (as defined in Section 11.1.3), and
- incidence of transfusion requirements.

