6.13 Efficacy Evaluation

As described in sec. 3.3 of the SAP, efficacy evaluation will be a secondary endpoint and refers to Phase II of the study.

Note: Considering that no hypothesis testing for difference between treatments groups was planned in the protocol, only 95% confidence intervals on differences between treatments will be presented and no p-values.

All secondary and the additional endpoint variables will be listed and summarized by treatment groups and at each time will be collected.

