6.13.6 Incidence of Treatment Failure

Incidence of treatment failure is defined on treatment failure criteria according to section 11.1.3 of the protocol:

- in case the bleeding at TBS (or re-bleeding) is still observed after 10 minutes following first application of study product;
- if hemostasis at TBS is achieved, but the Investigator decides that an additional treatment is required to ensure the durability of hemostasis;
- if there is a breakthrough bleeding requiring treatment other than the study product, at any time

Data will be presented only with the appropriate descriptive statistics and exact Clopper Pearson 95% confidence interval of the difference between treatments

	STATISTICAL ANALYSIS PLAN	FSTAT.01.03
Study Code: HEM-HEM-01-17		Sealantium Medical Ltd.

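### The SAP carries two definitions of treatment failure: section 3.3.2 exempts re-bleeding from patch movement or external causes, section 6.13.6 does not, and section 9 does not record the change

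*SAP*

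**What the plan says.** Protocol 11.1.3 defines treatment failure by three criteria: bleeding or re-bleeding at the target bleeding site (TBS) still seen after 10 minutes from first application; hemostasis reached, but further treatment judged necessary to make it last; and "if there is a breakthrough bleeding requiring treatment other than the product, at any time". The protocol synopsis gives the same three, and Protocol 14.8.2 refers back to 11.1.3. None of these places distinguishes events by cause.

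SAP 3.3.2 lists the same criteria and then narrows them: "From treatment failures definition are excluded those re-bleeding arising from the target bleeding site after hemostasis has been reached", if the re-bleeding was "caused by movement of patch from the wound (caused by the surgeon or any other possible external factor) or other external factors". It continues: "These cases should be regarded as Adverse Events rather than treatment failures". The source given is a sponsor memo of 12 April 2022, whose title calls it a clarification.

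SAP 6.13.6 sets out the analysis: "Incidence of treatment failure is defined on treatment failure criteria according to section 11.1.3 of the protocol". It restates the three criteria and stops there.

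SAP 9.1 records changes to the analysis sets. SAP 9.2 records one endpoint change, the added analysis of time to hemostasis from randomization (TTHR).

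**The concern.** One endpoint has two definitions in the same SAP, and they can give different counts from the same data. A programmer working from 6.13.6 would count an exempted re-bleed as a failure; a reader relying on 3.3.2 would assume it had been left out.

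Three features make this more than a missing cross-reference:

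- **Direction within an arm.** The exemption only removes events, so it can only lower an arm's failure rate.
- **Judgement of cause.** The trial is open-label. The SAP text does not delimit the residual category of external causes or say who assigns the cause, so the classification could be influenced by knowledge of the treatment.
- **Traceability.** Section 3 of the SAP is headed as reproducing the protocol, yet the exemption is not in protocol version 5.0, and the change list omits it. A reader of the study report could take the reported rate for the protocol's endpoint.

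**Working it through.** The point is settled mainly by comparing the texts.

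| Place | Three criteria | Exemption by cause | Memo cited |
|---|---|---|---|
| Protocol synopsis and 11.1.3 | yes | no | no |
| SAP 3.3.2 | yes | yes | yes |
| SAP 6.13.6 | yes, by reference to Protocol 11.1.3 | no | no |
| SAP 9.1 and 9.2 | not applicable | not listed | not listed |

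**Does the SAP say which text governs?** Section 6.13 opens with "As described in sec. 3.3 of the SAP, efficacy evaluation will be a secondary endpoint". That sentence refers back to 3.3 only to place efficacy among the secondary endpoints. Section 6.13.6 then cites the protocol and not 3.3.2. No order of precedence is given.

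**Which patients are affected?** The two definitions differ only for a patient who meets all of these conditions:

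1. Hemostasis was reached and the TBS then re-bled.
2. The cause is put down to patch movement or another external factor.
3. The event meets at least one of the three failure criteria.
4. No other event makes the patient a failure.

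For example, a re-bleed within 10 minutes that is controlled with another study patch, with no bleeding after 10 minutes, meets neither the first nor the third criterion. Unless the second criterion applies, it is not a failure under either text.

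**Was a later change allowed?** SAP section 2 ties the plan to protocol version 5.0 of 8 July 2021, about nine months before the memo. Protocol 14.6 expects the SAP to set out changes from the original statistical plan. The late date is therefore not irregular in itself. The change belongs in SAP section 9 and is not there.

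**Size.** The inputs are 15 planned patients per arm (Protocol 14.1, SAP 3.4) and the analysis sets in SAP 4.1. If *k* patients are reclassified among *n* analysed in an arm, the failure rate falls by *k/n*. For *k* = 1:

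- *n* = 15 (planned): 1/15 = 6.7 points
- *n* = 14, 13, 12 (assumed, for FAS1 or PPS after exclusions): 7.1, 7.7 and 8.3 points
- *n* = 16 (assumed, for FAS2 if a treated patient drops out and is replaced): 1/16 = 6.25 points

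For the difference sFilm-FS minus TACHOSIL, with *a* and *b* patients reclassified in the two arms, the shift is −*a*/*n*A + *b*/*n*B. With 15 per arm, one patient in the sFilm-FS arm only gives −6.7 points, one in the TACHOSIL arm only gives +6.7, and one in each gives 0.

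**Precision for scale.** The plan gives no expected failure rate. Its only worked interval is in Protocol 14.8.2, for hemostasis at 3 minutes: 12/15 = 80%, exact 95% interval 52% to 96%. Recomputed by Clopper-Pearson this is 51.9% to 95.7%, so the figure is reproduced. As an illustration with assumed failure counts, the same method gives:

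- 3/15 = 20.0% (4.3% to 48.1%)
- 2/15 = 13.3% (1.7% to 40.5%) with one patient reclassified
- 1/15 = 6.7% (0.2% to 31.9%) with two reclassified

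**The case against.** The best defence is that 3.3.2 and 6.13.6 can be read together. Section 3.3.2 defines the endpoint, openly cites a dated memo and adds a specific qualification; 6.13.6 merely restates the general rule. On that reading only a cross-reference and a change-log entry are missing. But 6.13.6 cites the protocol as its source, and the protocol lacks the qualification. The exemption also does more than clarify, since the first criterion expressly includes re-bleeding and the third applies at any time.

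On attribution, Protocol 13.1 has the investigator grade each adverse event's relationship to the product, and SAP 6.12 has a medical reviewer classify safety endpoints. This helps, but grading relationship to the product is not the same as deciding why a patch moved. The reviewer is not said to decide cause for this efficacy endpoint. The memo may define the terms and name the assessor; it is not among the documents, so this part of the concern cannot be taken further.

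On importance, several points stand. There is no hypothesis test, all results are called exploratory (SAP 6.6), and the step of about 7 points is small beside the 44-point width of the protocol's own example interval. Exempted events still appear in the adverse-event outputs (SAP 6.12.2 and 6.12.3). Under SAP 6.13.1, re-bleeding from 10 minutes to closure still counts against hemostasis, with no exception by cause. These points limit the harm but do not decide which failure rate is to be reported.

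Ranking one definition as main is partly a choice. Reporting both unranked would be defensible, since SAP 9.1 does not rank the analysis sets either. The reason for ranking is that the protocol definition was specified first and 6.13.6 already cites it.

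**Conclusion.** The concern holds. SAP 3.3.2 and 6.13.6 define treatment failure differently, the SAP does not say which applies, and section 9 omits the change.

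Each affected patient moves an arm's failure rate by 6.7 points at the planned 15. The step is between 6.25 and 8.3 points for assumed set sizes from 16 down to 12. The exemption can only lower an arm's rate, while its effect on the between-arm difference can go either way. How many patients are affected cannot be estimated from the documents and may be none.

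This should be fixed before database lock. It does not affect the sample size, the primary safety endpoint or the validity of the trial. The finding rests on the wording of the two documents alone and assumes no failure rate.

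**What to change.** - Make SAP 3.3.2 and 6.13.6 state the same definition.
- Use the Protocol 11.1.3 criteria for the main analysis, and report the memo definition as a labelled sensitivity analysis.
- List each exempted case by arm, with the stated cause and who assigned it. If the memo defines the external causes or names the assessor, bring that text into the SAP.
- Record the memo and its effect on the endpoint in SAP 9.2.

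The cost is a few sentences of SAP text, one short listing and one extra table, or up to three if the sensitivity analysis is run on FAS1, FAS2 and PPS as SAP 6.3 has it for efficacy. No new data collection is needed if cause and assessor were recorded with the adverse event; otherwise they must be queried. The drawback is that the main failure rate may be higher than under the memo, because re-bleeding caused by surgical handling then counts against the product. The sensitivity analysis shows how much of the rate that explains.
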